8.4.5. Hepatic Impairment

In subjects with hepatic impairment, the grade of impairment will be assessed by the investigator prior to randomization and as needed during the trial using the Child-Pugh system ([FDA, 2003](#)). For subjects assessed using the Child-Pugh system, it is important that impaired hepatic function, not another underlying disease, is the cause of alterations in the Child-Pugh components (bilirubin, albumin, prothrombin time, encephalopathy, and ascites). Scoring will be performed according to [Table 3](#) and the classification will be based on the total score;

- Class A (mild): 5 or 6 points

- Class B (moderate): 7 to 9 points
- Class C (severe): 10 to 15 points

Table 3. Child-Pugh System

	Points scored for observed findings		
	1	2	3
Encephalopathy grade ¹⁾	None	1 or 2	3 or 4
Ascites	Absent	Slight	Moderate
Total bilirubin ²⁾	<2 mg/dL (<34.2 µmol/L)	2 to 3 mg/dL (34.2 to 51.3 µmol/L)	>3 mg/dL (>51.3 µmol/L)
Serum albumin ²⁾	>3.5 g/dL (>35 g/L)	2.8 to 3.5 g/dL (28 to 35 g/L)	<2.8 g/dL (<28 g/L)
Prothrombin time, sec prolonged (or INR as below)	<4	4 to 6	>6
INR	<1.7	1.7 to 2.3	>2.3

- 1) Grade 0: normal consciousness, personality, neurological examination, electroencephalogram
Grade 1: restless, sleep disturbed, irritable/agitated, tremor, impaired handwriting, 5 cps waves
Grade 2: lethargic, time-disoriented, inappropriate, asterixis, ataxia, slow triphasic waves
Grade 3: somnolent, stuporous, place-disoriented, hyperactive reflexes, rigidity, slower waves
Grade 4: unrousable coma, no personality/behavior, decerebrate, slow 2-3 cps delta activity
- 2) If using results from the central laboratory for calculating the scores, the alternative units may have to be considered

8.4.6. Pregnancy Testing

Women of childbearing potential will undergo pregnancy tests (urine dip-sticks or serum if required by local regulations) at the screening and Day 15 visits or at the EWD visit if the subject is withdrawn prematurely. The outcome of the test will be reported as “positive” or “negative” in the eCRF. If the urine pregnancy test is positive, a blood pregnancy test will be performed to confirm positive pregnancy.

Women of non-childbearing potential are defined as pre-menopausal females who are sterilised (tubal ligation or permanent bilateral occlusion of fallopian tubes); or post-menopausal defined as 12 months of amenorrhea) (see Section 10.3).

Additional serum or urine pregnancy tests may be performed, as determined necessary by the investigator or required by local regulation, to establish the absence of pregnancy at any time during the subject’s participation in the trial.

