10.3. Appendix 3: Contraceptive and Barrier Guidance

10.3.1. Requirements

Contraceptive use by men and women must be consistent with local regulations regarding the methods of contraception for those participating in clinical studies and be according to the following gender specific requirements:

1. Male subjects are eligible to participate if they agree to the following during the IMP treatment period and for at least 2 weeks after the last dose of IMP:
 - i. Refrain from donating fresh unwashed semen
 - AND
 - ii. Must agree to use contraception/barrier as detailed below
 - iii. Agree to use a male condom and should also be advised of the benefit for a female partner to use a highly effective method of contraception as a condom may break or leak when having sexual intercourse with a woman) of childbearing potential (WOCBP) who is not currently pregnant
 - iv. Agree to use a male condom when engaging in any activity that allows for passage of ejaculate to another person
2. Female subjects are eligible to participate if she is not pregnant or breastfeeding, and the following conditions applies:
 - i. Is a woman of nonchildbearing potential (WONCBP) as defined in section [10.3.2. Contraception and Barrier Guidance](#).
 - ii. Is a WOCBP and using a contraceptive method that is highly effective (with a failure rate of <1% per year), preferably with low user dependency. Contraception and Barrier Guidance during the IMP treatment period and for at least 2 weeks after the last dose of IMP and agrees not to donate eggs (ova, oocytes) for the purpose of reproduction during this period. The investigator should evaluate the potential for contraceptive method failure (e.g., noncompliance, recently initiated) in relationship to the first dose of IMP.
 - iii. A WOCBP must have a negative highly sensitive pregnancy test (urine or serum) as required by local regulations) before the first dose of IMP (see Section [0](#)).
 - iv. If a urine test cannot be confirmed as negative (e.g., an ambiguous result), a serum pregnancy test is required. In such cases, the subject must be excluded from participation if the serum pregnancy result is positive.
 - v. Additional requirements for pregnancy testing during and after IMP treatment (see Section [8.5.5](#)).
 - vi. The investigator is responsible for review of medical history, menstrual history, and recent sexual activity to decrease the risk for inclusion of a woman with an early undetected pregnancy.

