10.3.2. Definitions

Women in the following categories are considered WOCBP (fertile):

- Following menarche
 - From the time of menarche until becoming postmenopausal unless permanently sterile (see below)
 - Permanent sterilization methods (for the purpose of this trial) include:
 - Documented hysterectomy
 - Documented bilateral salpingectomy
 - Documented bilateral oophorectomy
 - For individuals with permanent infertility due to an alternate medical cause other than the above, (e.g., Mullerian agenesis, androgen insensitivity, gonadal dysgenesis), investigator discretion should be applied to determining trial entry.

Note: Documentation can come from the site personnel's review of the subject's medical records, medical examination, or medical history interview.

- If fertility is unclear (e.g., amenorrhea in adolescents or athletes) and a menstrual cycle cannot be confirmed before first dose of IMP treatment, additional evaluation should be considered.

Women in the following categories are considered WONCBP:

- Premenopausal female with permanent infertility due to one of the following:
 - a. Documented hysterectomy
 - b. Documented bilateral salpingectomy
 - c. Documented bilateral oophorectomy
 - d. For individuals with permanent infertility due to an alternate medical cause other than the above, (e.g., Mullerian agenesis, androgen insensitivity, gonadal dysgenesis), investigator discretion should be applied to determining trial eligibility.

Note: Documentation can come from the site personnel's review of the subject's medical records, medical examination, or medical history interview.

- Postmenopausal female
 - a. A postmenopausal state is defined as no menses for 12 months without an alternative medical cause.
 - i. A high follicle stimulating hormone (FSH) level in the postmenopausal range may be used to confirm a postmenopausal state in women not using hormonal contraception or hormonal replacement therapy (HRT). However, in the absence of 12 months of amenorrhea, confirmation with more than one FSH measurement is required.

Females on HRT and whose menopausal status is in doubt should not be considered to be in a postmenopausal state.

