10.3.3. Contraception Guidance

CONTRACEPTIVES^a ALLOWED DURING THE TRIAL INCLUDE:

Highly Effective Methods^b That Have Low User Dependency

- Implantable progestogen-only hormone contraception associated with inhibition of ovulation^c
- Intrauterine device (IUD)
- Intrauterine hormone-releasing system (IUS)^c
- Bilateral tubal occlusion
- Azoospermic partner (vasectomized or due to a medical cause)

Azoospermia is a highly effective contraceptive method provided that the partner is the sole sexual partner of the woman of childbearing potential and the absence of sperm has been confirmed. If not, an additional highly effective method of contraception should be used. Spermatogenesis cycle is approximately 90 days. Note: documentation of azoospermia for a male subject can come from the site personnel's review of the subject's medical records, medical examination, or medical history interview.

Highly Effective Methods^b That Are User Dependent

- Combined (estrogen- and progestogen-containing) hormonal contraception associated with inhibition of ovulation^c
 - oral
 - intravaginal
 - transdermal
 - injectable
- Progestogen-only hormone contraception associated with inhibition of ovulation^c
 - oral
 - injectable

a) Contraceptive use by men or women should be consistent with local regulations regarding the use of contraceptive methods for those participating in clinical studies.

b) Failure rate of <1% per year when used consistently and correctly. Typical use failure rates differ from those when used consistently and correctly.

c) If locally required, in accordance with Clinical Trial Facilitation Group (CTFG) guidelines, acceptable contraceptive methods are limited to those which inhibit ovulation as the primary mode of action.

Note: Periodic abstinence (calendar, symptothermal, postovulation methods), withdrawal (coitus interruptus), spermicides only, and lactational amenorrhea method (LAM) are not acceptable methods of contraception for this trial. Male condom and female condom should not be used together (due to risk of failure from friction).

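### Protocol 8.4.6 counts pre-menopausal women with tubal ligation or occlusion as non-childbearing, against Appendix 3, so their only scheduled pre-dose pregnancy test could be omitted (minor)

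*Protocol*

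**What the plan says.** Protocol 8.4.6 decides who is tested: "Women of childbearing potential will undergo pregnancy tests", at screening and at Day 15, or at the early withdrawal visit. Footnote 13 of the Schedule of Activities (1.3) has the same restriction. Section 8.4.6 then gives its own definition of non-childbearing potential. The pre-menopausal part of it is "pre-menopausal females who are sterilised (tubal ligation or permanent bilateral occlusion of fallopian tubes"; the other part is 12 months of amenorrhea. The sentence ends with a pointer to Section 10.3. The section also allows unscheduled testing: "Additional serum or urine pregnancy tests may be performed, as determined necessary by the investigator or required by local regulation".

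Appendix 3 defines the same groups again:

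- **10.3.1:** "A WOCBP must have a negative highly sensitive pregnancy test" before the first dose.
- **10.3.2, WOCBP:** a woman is a WOCBP from menarche to menopause unless permanently sterile. "Permanent sterilization methods (for the purpose of this trial) include" documented hysterectomy, bilateral salpingectomy and bilateral oophorectomy. For permanent infertility from another medical cause, "investigator discretion should be applied to determining trial entry".
- **10.3.2, non-childbearing (WONCBP):** "Premenopausal female with permanent infertility due to one of the following", followed by the same three procedures and the same discretionary item.
- **10.3.3:** "Bilateral tubal occlusion" is an allowed contraceptive method, in the highly effective, low user dependency group.

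**The concern.** The same procedure takes a woman out of the testing group in 8.4.6 and serves as her contraception in 10.3.3. Only a woman who could otherwise conceive needs contraception, so the two sections put her in different classes.

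The class decides whether she gets a mandatory safety step. A WOCBP must have a negative test before dosing, while a non-childbearing woman has no scheduled test. The Schedule of Activities has no pregnancy test on Day 1, so screening is the only scheduled pre-dose test. The next is at Day 15 or early withdrawal, and by Day 15 the 14-day course is over. A site that takes its definition from 8.4.6 could dose a woman untested when 10.3.1 requires a test.

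**Working it through.** The plan states no figure on this point, so the check is a comparison of texts followed by a bound on size.

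**Comparison for a pre-menopausal woman with a tubal procedure**

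| Source | Bilateral tubal occlusion | Tubal ligation |
|---|---|---|
| 8.4.6 | Non-childbearing, no scheduled test | Non-childbearing, no scheduled test |
| 10.3.2 | Not among the named sterilization methods | Not among the named sterilization methods |
| 10.3.3 | A contraceptive method, so the user is a WOCBP | Not named |
| 10.3.1 | Negative pre-dose test required | Required if she is a WOCBP |

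Two points limit the reading. The 10.3.2 list is not fully closed, because it leaves infertility from another medical cause to the investigator. Tubal ligation does not appear by name in Appendix 3, so its WOCBP status there is inferred from its absence from 10.3.2 and from the entry for occlusion. For occlusion, 10.3.3 leaves little doubt.

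The mismatch also runs the other way. Section 8.4.6 omits hysterectomy, salpingectomy and oophorectomy, but following it there would only add harmless tests.

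**Which text controls.** Section 8.4.6 points to 10.3, and inclusion criterion 4 (5.1) applies Appendix 3. Appendix 3 therefore controls, and the tubal wording in 8.4.6 is the text to correct.

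**Size.** Two inputs come from the Protocol: at most 300 subjects (1.1) and 75.5% males in the phase 2 trial (2.2). The rest are assumptions for illustration and are not in the documents: the phase 2 sex mix carries over, 10% to 40% of the women are pre-menopausal, and 10% to 30% of those have had tubal ligation or occlusion.

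- Women enrolled: 300 × (1 − 0.755) = 73.5. This is the ceiling if the sex mix holds.
- Low end: 73.5 × 0.10 × 0.10 = 0.735, which is 0.735 / 300 = 0.2% of subjects.
- High end: 73.5 × 0.40 × 0.30 = 8.82, which is 8.82 / 300 = 2.9% of subjects.
- On C21 under 1:1 allocation: 0.735 / 2 = 0.4 to 8.82 / 2 = 4.4 women.

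These are women whose test might be omitted, not missed pregnancies. Footnote b of 10.3.3 gives a failure rate below 1% per year with consistent and correct use. Applied to the high end, and extended to ligation by assumption, this gives fewer than 8.82 × 0.01 = 0.09 conceptions per year over both arms.

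**The case against.** The strongest reply is that the protocol already resolves the conflict and that almost nobody would be harmed. Section 8.4.6 sends the reader to 10.3, inclusion criterion 4 applies Appendix 3, and the Schedule of Activities says only that testing applies to women of childbearing potential, without repeating the tubal wording. Pregnant women are excluded in any case (exclusion criterion 10). Investigators must review menstrual history and recent sexual activity (10.3.1) and may add tests. The women concerned use a method that the protocol rates as failing in fewer than 1% per year. The illustrative counts rest on proportions that are not in the documents. An amendment may also come too late: Protocol version 5.0 is dated 13 April 2022, the SAP carries a signature dated 24 August 2022, and neither document says how many subjects remained to be enrolled.

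Most of this stands as a limit on weight. A missed test is unlikely and a missed pregnancy more so, and the counts show only an order of magnitude.

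It does not remove the conflict. The pointer to 10.3 follows a definition that looks complete, so a reader has no reason to expect a different one there. The history review does not replace the test that the same section makes mandatory, and extra tests are discretionary unless local rules require them. Exclusion criterion 14, a positive test, cannot act on a woman who was not tested. The way back from Appendix 3 is also weak: 10.3.1 refers to 8.5.5 for further testing requirements, but 8.5.5 deals with pregnancy reporting and contains none.

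**Conclusion.** The concern holds, as a minor point. The two definitions conflict in the current protocol. For bilateral tubal occlusion the conflict is plain on the page; for tubal ligation it is a well-supported inference. A literal reading of 8.4.6 could drop the only scheduled pre-dose test in women for whom Appendix 3 makes that test mandatory.

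The number affected is small and cannot be derived from the documents. The range of 0.7 to 8.8 women depends wholly on the stated assumptions. Subjects already enrolled reduce the number that a correction can reach. No estimand, efficacy analysis, type I error rate or power is affected. The gain is a small one in subject safety.

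**What to change.** Delete the definition of non-childbearing potential in Protocol 8.4.6 and refer instead to WONCBP as defined in Section 10.3.2. Women with tubal ligation or occlusion are then tested before first dose. The fuller postmenopausal definition of 10.3.2 then applies as well: no alternative medical cause, the conditions for FSH confirmation, and the rule for women on hormone replacement. Section 8.4.6 reduces all of this to amenorrhea alone. Notify sites of the change.

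The cost is one sentence, a site notice and a few urine dipsticks (for 0.7 to 8.8 women under the assumptions above). Section 10.1.1 requires IRB/IEC approval before an amendment takes effect, so the change is best bundled into the next amendment. The SAP needs no change.

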8.4.7. SARS-CoV-2 Variant

Oropharyngeal swabs will be collected as outlined in the SoA (see Section 1.3). A central laboratory will determine the SARS-CoV-2 variant.

8.4.8. New Infections

Information on new infections (viral and non-viral) should be reported as AEs. Information should preferably include the site of infection and source of culture.

8.5. Adverse Events, Serious Adverse Events, and Other Safety Reporting

The definitions of AEs and SAEs can be found in Appendix 2 (see Section 10.2).

AEs will be reported by the subject (or, when appropriate, by a caregiver, surrogate, or the subject's legally authorized representative).

The investigator and any qualified designees are responsible for detecting, documenting, and recording events that meet the definition of an AE or SAE and remain responsible for following up all AEs OR AEs that are serious, considered related to the IMP or trial procedures, or that caused the subject to discontinue the IMP or trial (see Section 7).

The method of recording, evaluating, and assessing causality of AEs and SAEs and the procedures for completing and transmitting SAE reports are provided in Appendix 2 (see Section 10.2).

8.5.1. Time Period and Frequency for Collecting AE and SAE Information

All AEs will be collected from signing of the ICF until Day 29 at the timepoints specified in the SoA (see Section 1.3). SAEs will further be collected until Day 60. All AEs are followed until they have reached a final outcome (see Section 10.2) or the subject's participation in the trial ends, whichever comes first.

All SAEs will be recorded and reported to the sponsor or designee immediately and under no circumstance should this exceed 24 hours after SAE awareness, as indicated in Appendix 2 (see Section 10.2). The investigator will submit any updated SAE data to the sponsor within 24 hours of it being available.

Information on SAEs must be entered in the eCRF.

Investigators are not obligated to actively seek information on AEs or SAEs after conclusion of the trial participation. However, if the investigator learns of any SAE, including a death, at any time after a subject has been discharged from the trial, and he/she considers the event to be reasonably related to the IMP or trial participation, the investigator must promptly notify the sponsor regardless of the time that has elapsed (post-trial events).

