The SARS-CoV-2 virus is known to bind to and enter target cells through angiotensin converting enzyme (ACE) 2, an integral component of the renin-angiotensin system (RAS) ([Zhang et al., 2020](#)). Within the RAS, the Angiotensin II type 1 receptor (AT1R) normally mediates the classical actions of Angiotensin II, including constriction of blood vessels, sodium retention and cell growth, while abnormal AT1R activation contributes to the pathogenesis of certain cardiovascular, renal and pulmonary diseases ([de Man et al., 2012](#); [Savoia & Schiffrin, 2006](#); [Summers et al., 2019](#)). Conversely, activation of the AT2R causes dilatation of blood vessels and inhibition of inflammation and fibrosis, and is considered to be counter-regulatory to the negative effects of AT1R activation ([Matavelli et al., 2015](#); [Summers et al., 2019](#)).

While the AT2R is only expressed at low levels in most tissues in healthy adults ([De Gasparo, 2002](#); [Steckelings et al., 2005](#)), it is highly expressed in alveolar type 2 progenitor cells in the adult human lung and can be upregulated during repair and regeneration ([Akishita et al., 1999](#); [Protein-Atlas](#)). This, coupled with the belief that the RAS may play a key role in the development of COVID-19 led us to the view that C21 may have a role in the treatment of the disease by directly activating AT2R downstream of ACE2, thus by-passing any inherent negative effects in the infected state.

The safety and efficacy of C21 in subjects with COVID-19 were investigated in a randomized, double-blind, placebo-controlled, phase 2 trial (VP-C21-006). The trial included 106 adult subjects hospitalized with COVID-19, having a CRP between 50-150 mg/L and not in need of mechanical ventilation. The subjects were randomized to receive oral treatment with C21 (100 mg b.i.d., n=51) or placebo (n=56) for 7 days on top of standard of care. All subjects were followed up for 7 to 10 days after receiving the last investigational medicinal product (IMP) dose.

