2.3.1. Risk Assessment

Potential Risk of Clinical Significance	Summary of Data/Rationale for Risk	Mitigation Strategy
IMP - C21		
Alopecia	
Reversible alopecia was observed in subjects who received 200 mg b.i.d. for 8 days in a phase 1 trial, C21-003. Alopecia was not observed in the VP-C21-006 trial (51 subject treated with 100 mg b.i.d. for 7 days). Further information can be found in the IB.
	
No mitigation strategy implemented due to the severity of the COVID-19 disease in the trial population and the low risk of developing alopecia at the selected dose and treatment duration (100 mg b.i.d. for 14 days).

Drug-drug interactions	
C21 is metabolized primarily by CYP3A4.
	
Exclusion of subjects treated with strong CYP3A4 inducers and/or with Warfarin.

	
In vitro data show that a clinically relevant interaction with CYP enzymes (e.g., CYP2C9, CYP3A4 and CYP1A2) and efflux transporters (multi-drug resistance gene (MDR1) and breast cancer resistance protein (BCRP)) cannot be excluded.
	
The medical monitor and the DMC will monitor the extent of co-administration with CYP1A2, CYP3A4 and CYP2C9 substrates with a narrow therapeutic index and will inform the investigator if sub-optimal combinations occur.
 
Exclusion of subjects treated with P-gp substrates with narrow therapeutic index, high dose BCRP sensitive substrates, and sulphasalazine or rosuvastatin.

Drug-food interactions	
Exposure of C21 was substantially decreased under fed conditions as compared to fasted conditions indicating an interaction with food (VP-C21-003).
	
IMP will be administered in fasting conditions (see Section 5.3).
 
Correct administration of IMP in relation to food intake will be monitored during the trial.

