4.3. Justification for Dose

Subjects will be treated with oral 100 mg C21 or placebo b.i.d. for 14 days.

The results of the completed phase 2 trial in COVID-19 subjects (VP-C21-006) and of the phase 1 trial in healthy subjects (VP-C21-003) indicate an acceptable safety and tolerability profile for the 100 mg b.i.d. dose. The risks of C21 in adults are considered primarily related to reversible alopecia seen at the higher dose of 200 mg b.i.d. In the phase 2 trial in COVID-19 subjects (VP-C21-006) and the phase 1 trial (VP-C21-003), the 100 mg b.i.d. dose did not cause any hair loss (Further details can be found in the IB). Alopecia is therefore not considered to present any significant safety risk to subjects in this trial.

In the phase 1 trial (VP-C21-003), 100 mg b.i.d. dosing prolonged the duration of the plasma concentration at therapeutic relevant levels. After oral administration, C21 was rapidly absorbed. On Day 8, median t_{max} was 0.33 hours after each dose post-dose, and C21 was measurable in plasma until 4-6 hours after the first and second dose. Lower doses than 100 mg b.i.d. may not provide maximal efficacy benefit.

In the completed phase 2 trial (VP-C21-006) in COVID-19 subjects, treatment with 100 mg b.i.d. for 7 days, reduced the need for extended oxygen supplementation.

The recently completed phase 2 trial (VP-C21-006) indicates that C21 can prevent hypoxic critical illness and based on the course of the disease, there is a strong rational to extend the treatment duration from 7 to 14 days. Furthermore, 27% of subjects within the C21 arm were still in need of oxygen (vs 45% on placebo) at the end of the 7 days treatment, highlighting an opportunity to treat for a longer period to gain additional benefit, with the aim of returning patients to normoxia.

There is not enough evidence to treat beyond 14 days at this stage.

Based on the above, C21 will be administered at an oral dose of 100 mg b.i.d. for 14 days in the present trial.

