8.4.1. Physical Examinations

- Physical examinations will be performed as outlined in the SoA (see Section 1.3).
- The physical examination will include assessments of the respiratory and cardiovascular systems. Other systems will be assessed per investigator judgment.
- Investigators should pay special attention to clinical signs related to previous serious illnesses.
- Each body system will be reported as “normal” or “abnormal”. Any clinically significant abnormalities prior to initiation of IMP should be specified and recorded as medical history. New clinically significant abnormalities occurring after initiation of IMP should be reported as AEs.

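### New non-serious adverse events, including alopecia (the risk the protocol itself ranks first for C21), are not collected after Day 29, although subjects are still contacted on Day 60

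*Protocol*

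**What the plan says.** **Collection window.** Protocol 8.5.1 sets the general rule, "All AEs will be collected from signing of the ICF until Day 29 at the timepoints specified in the SoA (see Section 1.3", and then adds "SAEs will further be collected until Day 60". Footnote 10 of the Schedule of Activities (SoA, Protocol 1.3) restricts the adverse-event entry at the Day 60 visit to SAEs. SAP Table 1 reproduces the same schedule and footnote.

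**Follow-up of events already recorded.** The same section says "All AEs are followed until they have reached a final outcome" or the subject's participation ends. Protocol 8.5.3 and 10.2.3 support this, and 10.2.3 asks for related non-serious events to be followed until the outcome is established.

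**Alopecia.** Protocol 2.3.1 reports: "Reversible alopecia was observed in subjects who received 200 mg b.i.d. for 8 days in a phase 1 trial". It plans no mitigation, citing the severity of COVID-19 and "the low risk of developing alopecia at the selected dose and treatment duration (100 mg b.i.d. for 14 days". Section 4.3 ranks reversible alopecia first among the risks of C21, ties it to the 200 mg b.i.d. dose, notes no hair loss at 100 mg b.i.d. in phases 1 and 2, and concludes: "Alopecia is therefore not considered to present any significant safety risk to subjects in this trial".

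**Prior data at 100 mg b.i.d.** Phase 2 treated 51 subjects for 7 days without alopecia (2.3.1), and "All subjects were followed up for 7 to 10 days after receiving the last investigational medicinal product (IMP) dose" (2.2). Section 2.2 gives 8 days as the longest duration at up to 100 mg b.i.d.

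**Analysis.** SAP 12.6.1 allows risk differences for selected preferred terms chosen before database lock. It does not name alopecia.

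**The concern.** The protocol singles out one adverse effect, yet its collection rule closes to new cases of that effect halfway through follow-up. Subjects are still reached on Day 60, but hair loss that began after Day 29 has no place in the scheduled record unless it is serious.

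This matters because the trial is the first among those cited to give 100 mg b.i.d. for 14 days. The low-risk statement for that duration extrapolates from about half as many dosing days, so the trial's own safety data are the first chance to check it. A short onset window weakens that check.

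Capture before Day 29 is also largely passive. On the Day 15 examination, Protocol 8.4.1 says: "The physical examination will include assessments of the respiratory and cardiovascular systems". Other systems are left to the investigator. For discharged subjects, Days 22 and 29 are phone or video contacts.

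**Working it through.** **The plan's own figure.** The SAP 12.3.1 dose formula uses 56 dispensed capsules of 50 mg. Protocol 6.1 gives 4 capsules a day: 4 × 14 = 56, which agrees. 56 × 50 mg = 2,800 mg.

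**Uncaptured time.** Inputs are last dose Day 14 (Protocol 6.1, Table 1), general AE collection to Day 29, and last contact Day 60 (8.5.1, SoA).
- Last dose to end of general AE collection: 29 − 14 = 15 days.
- Last dose to last contact: 60 − 14 = 46 days.
- Days without capture of new non-serious onset: 60 − 29 = 31 days; 31/46 = 67%.
- The Day 60 visit has a window of ±3 days, so the gap is 28 to 34 days.

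**Exposure.** Total dose = mg per dose × 2 × days.

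| Regimen | Total dose | Share of 3,200 mg | Daily dose |
|---|---|---|---|
| Alopecia regimen, 200 mg b.i.d. × 8 days | 3,200 mg | 100% | 400 mg |
| This trial, 100 mg b.i.d. × 14 days | 2,800 mg | 87.5% | 200 mg |
| Longest prior use at 100 mg b.i.d., 8 days | 1,600 mg | 50% | 200 mg |
| Phase 2, 100 mg b.i.d. × 7 days | 1,400 mg | 43.75% | 200 mg |

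This trial gives 88% of the total dose of the alopecia regimen at 200/400 = 50% of its daily dose. It gives twice the phase 2 total.

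**What 0 of 51 can exclude.** The one-sided 95% upper limit is 1 − 0.05^(1/51) = 5.7%; the two-sided limit is 1 − 0.025^(1/51) = 7.0%. Both apply to a 7-day course with short follow-up. They omit the phase 1 subjects on 100 mg b.i.d., whose number the documents do not give; adding them would lower the limits.

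**What cannot be computed.** The number of cases starting on Days 30 to 60 needs the distribution of onset times. The documents do not give it.

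**A related inconsistency.** The SoA marks adverse events at unscheduled visits without brackets and without the SAE-only footnote. Footnote 3 gives a re-admission after Day 29 as an example of such a visit. Read literally, a non-serious event could be recorded there after Day 29, which does not fit 8.5.1.

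**The case against.** **Recorded cases are followed.** A reader might infer that alopecia goes unrecorded in this trial, or that nothing about it can be reported after Day 29. The documents do not support that. Onset up to Day 29 is recorded, and those cases are followed to outcome or end of participation. Only new onset is lost.

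**The 88% proves little alone.** It is tempting to read it as meaning that subjects receive nearly the dose that causes hair loss. No section says total dose is the driver. Section 4.3 links alopecia to the higher dose level, and the daily dose here is half. The total and daily comparisons belong together.

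**No count of missed cases is available.** One could assume a fraction of late onset and apply it to the 5.7% or 7.0% limit, but no such fraction has a source in the documents.

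**The choice was considered.** The protocol discusses alopecia and gives reasons for no mitigation. Fifteen days of full capture after the last dose exceeds the 7 to 10 days in phase 2. The prior treatment durations are stated openly. Hair loss is something subjects notice, and they are asked about adverse events at each visit. The SAP provides preferred-term tables, a listing of all events, and optional risk differences.

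All of this stands and limits the point. It does not show that onset is confined to the first 15 days after dosing, and it does not explain why a contact already scheduled should leave out new non-serious events.

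**Conclusion.** The gap is real and narrow. New-onset non-serious adverse events, alopecia among them, have no scheduled collection for the last 31 of 46 post-dose days. The protocol's low-risk statement for 14 days rests on 7 to 8 days of dosing at 100 mg b.i.d. and, in phase 2, 7 to 10 days of follow-up.

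The day counts assume a last dose on Day 14 and a visit on Day 60 itself. The conclusion also takes hair loss to be non-serious, which is usual but which the documents do not state. How many cases would be missed, possibly none, cannot be determined from the documents. The primary analysis is unaffected. The consequence is that a finding of little or no alopecia would describe onset only up to 15 days after the last dose, and should be reported with that limit if the plan stays as it is.

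**What to change.** 1. **Protocol 8.5.1 and SoA footnote 10, with the copy in SAP Table 1.** Record new-onset hair loss with its onset date, or any new adverse event, at the existing Day 60 contact in addition to SAEs. Reconcile this with the unbracketed adverse-event entry at unscheduled visits.
2. **SAP 12.6.1.** Name alopecia among the preferred terms that receive a risk difference with 95% CI, covering events up to Day 60. The treatment-emergent definition in SAP 10.6 has no end date, so the added records enter the existing tables without redefinition.

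**Cost.** One recorded item at a contact already scheduled, a footnote change and a sentence in the SAP. Dosing, visits and the primary analysis stay as they are.

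**Downsides.** Background hair loss after acute illness will also be recorded; the blinded placebo arm controls for it. A targeted question departs from the open questioning preferred in Protocol 8.5.2, so it should be worded identically in both blinded arms or put after the open question.
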